#### 4.4.9 Timelines and Reporting of Serious Adverse Events

Any SAE (see [Section 4.4.6](#)) that occurs after signing the ICF through the last day of subject's participation in the clinical trial must be expeditiously reported whether or not considered attributable to the study drug. Each SAE must be fully recorded in the subject's eCRF or SAE Report form.

SAEs will be reported using the designated SAE Report form. When the Investigator becomes aware of an SAE, she/he must submit electronically through EDC system or when EDC system is not available submit a completed, signed and dated SAE Report Form (in English) within 24 hours to the Sponsor by email/fax.

Each SAE must be followed up until resolution or stabilization. After the initial report, all relevant information for SAE follow up, and for the outcome, must also be supplied to the Sponsor in a timely manner (within 3 days from its identification or within 24 hours for relevant new information) by means of the SAE Report Form. In addition, the Sponsor or CRO may request additional information and/or reports.

All SAE Report Forms must be reported to Grifols electronically through EDC system or when EDC system is not available, reported to:

Grifols Global Pharmacovigilance

Email: [REDACTED]  
FAX (back-up only): [REDACTED]  
and [REDACTED]

When required, and according to local law and regulations, SAEs must be reported to the IRB/EC and regulatory authorities.

#### 4.4.10 Type and Duration of the Follow-Up of Subjects after Adverse Event or Suspected ADR

In so far as is possible, all individuals will be followed up until the AE or suspected ADR has been resolved. If an AE/suspected ADR/SAE is present when the subject has completed the study, the course of the event must be followed until the final outcome is known or the event has been stabilized and no further change is expected and the Investigator decides that no further follow-up is necessary.

Any pregnancy must be followed by the Investigator until delivery or to the end of pregnancy.

### 5 STATISTICAL METHODS AND DETERMINATION OF SAMPLE SIZE

#### 5.1 Statistical and Analytical Plans

Unless otherwise specified, descriptive statistics will include the number of non-missing observations, mean, standard deviation (SD), median, minimum and maximum values for the continuous/quantitative data or absolute and relative frequency counts and percentages for categorical/qualitative data.

Data handling and evaluation procedures will be described in the Statistical Analysis Plan.

##### 5.1.1 Subject Population(s) for Analysis

###### **Safety Population**

The Safety population consists of all subjects who received any amount of IP.

###### **Evaluable Population**

The evaluable population consists of all subjects who received the entire dose of IP (2 g/kg over 2 consecutive days) and had valid Baseline and Day 14 QMG Score measurements.

Any deviations from the protocol will be recorded in the protocol deviation list. The validity of a subject for inclusion in each of these two populations (safety and evaluable) will be assessed at a review meeting that will take place before finalizing the database. The review meeting will review the protocol deviation list, as well as data listings. If additional protocol deviations are identified which justify removing a subject from any population, then these decisions will be documented.

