#### 5.1.3.1 Primary Efficacy Analyses

The primary efficacy variable is the change from Baseline in QMG score at Day 14. The primary efficacy variable will be summarized. A paired t-test (comparison between the pre and post) will be used to test for the treatment effect. The hypothesis test is to test the null hypothesis:  $H_0: \mu_d = 0$  versus alternative hypothesis  $H_a: \mu_d \neq 0$  where  $\mu_d$  is the mean change from Baseline to Day 14.

If the assumptions for parametric test are not met, the non-parametric test (Wilcoxon signed rank test) will be used.

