#### 5.1.3.2 Secondary Efficacy Analyses

The following secondary efficacy variables will be summarized for evaluable population:

- Percentage of subjects who experience a clinical improvement assessed by QMG from Baseline (Day 0) to Day 14 where clinical improvement is defined as at least 3 point decrease in QMG
- Percentage of subjects who experience a clinical improvement assessed by MG-ADL from Baseline (Day 0) to Day 14 where clinical improvement is defined as at least 2 point decrease in MG-ADL
- Percentage of subjects who experience a clinical improvement assessed by the MG Composite from Baseline (Day 0) to Day 14 where clinical improvement is defined as at least 3 point decrease in the MG Composite

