4.2.2 Safety Study Variables

The following safety study variables will be assessed in this study:

- AEs, Suspected adverse drug reactions (Suspected ADRs), adverse reactions (ARs), Serious AEs (SAEs), and discontinuations due to AEs and SAEs.
- Vital Signs. Abnormal findings judged as clinically relevant by the Investigator will be considered AEs. Clinically relevant changes as determined by the

CONFIDENTIAL

Investigator in vital signs (temperature [T], respiratory rate [RR], heart rate [HR], systolic blood pressure [SBP] and diastolic blood pressure [DBP]) during infusions will be considered AEs temporally associated to the infusion.

- Physical Assessments. Physical exams will be recorded as normal or abnormal, according to the physician's judgment criteria. Abnormal findings judged by the Investigator as clinically relevant will be considered AEs.
- Blood biochemistry and haematology. Laboratory results out of the normal range that are judged by the Investigator as clinically relevant will be considered AEs.
- Thromboembolic events risk.
- Hemolysis detection.

5 General Statistical Considerations

All analyses will be conducted using SAS Version 9.4 or higher.

Unless otherwise noted, for continuous variables, descriptive statistics will include the number of non-missing values, mean, standard deviation, median, minimum and maximum. For categorical variables, descriptive statistics will include counts and percentages per category. The statistical inferences on efficacy data analyses will be tested at 2-sided with $\alpha=0.05$, if applicable. Additional details regarding the efficacy data analyses can be found in Section 10.

Unless otherwise noted, all data collected in the electronic case report forms or electronically transferred (such as central laboratory data) will be presented in data listings. Subjects will be identified in the data listings by subject number (which includes site number) and visit/time point.

For table summaries, the data will be presented at the scheduled visits according to protocol. Any data collected at the unscheduled visits will be listed.

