5.1 Data Handling

Unless otherwise noted, if an observation is missing at a specific scheduled visit/time point, the value at that visit/time point will not be imputed and will be set to missing.

Baseline in general will be defined as the last non-missing measurement taken prior to the start of the study drug infusion.

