5.2 Analysis Populations

Safety Population

The Safety population consists of all subjects who received any amount of investigational product (IP).

Evaluable Population

The evaluable population consists of all subjects who received the entire dose of IP (2 g/kg over 2 consecutive days) and had valid Baseline and Day 14 QMG Score measurements.

Any deviations from the protocol will be recorded in the protocol deviation list. The validity of a subject for inclusion in each of these two populations (safety and evaluable) will be assessed at a review meeting that will take place before finalizing the database. The review meeting will review the protocol deviation list, as well as data listings. If additional protocol deviations are identified which justify removing a subject from any population, then these decisions will be documented.

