9.3 Treatment Compliance

Treatment compliance will be listed and summarized by day and overall across the 2 days. The number of subjects with compliance less than 80% will be summarized by day and overall across the 2 days. Treatment compliance will be calculated as total actual volume infused * 100% / total volume prepared by day and overall across the 2 consecutive days. The total volume prepared is collected on the electronic case report form and is calculated based on the subject's weight at baseline. The total volume prepared and dispensed by pharmacist is the intended dose volume a subject should be given based on the body weight.

10 Efficacy Analysis

Efficacy Analyses

Efficacy data will be summarized by visit on evaluable population and safety population (if different).

Primary Efficacy Analyses

The primary efficacy variable is the change from Baseline in QMG score at Day 14. The primary efficacy variable will be summarized. A paired t-test (comparison between the pre and post) will be used to test for the treatment effect. The 95% confidence interval (CI) will be calculated. The hypothesis test is to test the null hypothesis: $H_0: \mu_d = 0$ versus alternative hypothesis $H_a: \mu_d \neq 0$ where μ_d is the mean change from Baseline to Day 14.

If the assumptions for parametric test are not met, the non-parametric test (Wilcoxon signed rank test) will be used. Shapiro-Wilk test will be used to test the normality.

Secondary Efficacy Analyses

The following secondary efficacy variables will be descriptively summarized:

- Percentage of subjects who experience a clinical improvement assessed by QMG from Baseline (Day 0) to Day 14 where clinical improvement is defined as at least 3 point decrease in QMG
- Percentage of subjects who experience a clinical improvement assessed by MG-ADL from Baseline (Day 0) to Day 14 where clinical improvement is defined as at least 2 point decrease in MG-ADL
- Percentage of subjects who experience a clinical improvement assessed by the MG Composite from Baseline (Day 0) to Day 14 where clinical improvement is defined as at least 3 point decrease in the MG Composite

Exploratory Efficacy Analyses

Summary statistics will be provided and paired t-test or Wilcoxon signed rank test will be used for testing the treatment effect (if applicable) at different visits for:

- Change in QMG score from Baseline (Day 0) to Day 7, Day 21 and Day 28
- Change in MG-ADL from Baseline (Day 0) to Day 7, Day 14, Day 21 and Day 28

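### Subjects who die or withdraw before Day 14 contribute nothing to the primary mean change in either efficacy set, and no pre-specified analysis accounts for them

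*Protocol*

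**What the plan says.** Protocol Section 5.1.1 admits to the Evaluable population only subjects who "received the entire dose of IP (2 g/kg over 2 consecutive days) and had valid Baseline and Day 14 QMG Score measurements". SAP Section 5.2 uses the same definition.

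For the primary variable, change in QMG from Baseline to Day 14, Protocol Section 5.1.3.1 states: "A paired t-test (comparison between the pre and post) will be used to test for the treatment effect". SAP Section 10 repeats this and adds a 95% confidence interval. On missing data, SAP Section 5.1 says that "the value at that visit/time point will not be imputed and will be set to missing" unless otherwise noted, and nothing different is noted for efficacy.

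Protocol Section 5.1.3 and SAP Section 10 send efficacy to both sets. In the SAP's words: "Efficacy data will be summarized by visit on evaluable population and safety population (if different"). For the three Day 14 responder endpoints, Protocol Section 5.1.3.2 names one set only: "The following secondary efficacy variables will be summarized for evaluable population". The SAP's secondary list names none. SAP Section 5 gives the general rule "For categorical variables, descriptive statistics will include counts and percentages per category" without saying which denominator applies.

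Protocol Section 3.10 asks dosed subjects who leave early to come back for a final visit about 28 days after their last infusion. That visit includes a QMG, but no rule assigns it to Day 14.

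**The concern.** A paired difference needs both scores. Moving from the Evaluable to the Safety population brings back incompletely dosed subjects who have both scores. It cannot bring back a subject with no Day 14 QMG. The primary mean change in both sets is therefore an estimate among subjects still under assessment at Day 14.

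The study enrols only MGFA class IVb or V exacerbations and has no control arm, so the mean change and the responder rates are the efficacy result. Protocol Section 3.9 requires withdrawal for, among other things, an adverse event judged to need termination of treatment, or an intercurrent condition whose severity or change in treatment conflicts with the study. It is plausible, although the documents do not say so, that some subjects who do badly leave by these routes or die. If so, both estimates lean toward benefit, and no comparator offsets this. The plan has no missing-data sensitivity analysis and no rule for how deaths or withdrawals enter the efficacy analysis. The Wilcoxon fallback deals with non-normality, not with missing scores.

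**Working it through.** **Inputs from the documents.** 50 subjects planned; SD of change 6.0; mean improvement 3.5; 90% power; n = 33 (Protocol Section 5.2, SAP Section 5.3). Two-sided alpha 0.05 (SAP Section 5).

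**Assumptions, because the documents give no loss rate.** All 50 are dosed and have a Baseline QMG; k = 5 or 10 lack a Day 14 score; observed subjects have mean change -3.5 and SD 6; about 70% of observed subjects respond; missing subjects have a fixed change d.

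**Step 1: the plan's own figure.** One-sample t-test, noncentrality (3.5/6) x sqrt(n). With n = 33 power is 90.1%, and with n = 32 it is 89.2%. The stated 33 is reproduced.

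**Step 2: is power at risk?** Power is 96.9% with 45 pairs and 94.9% with 40. It stays at 90% until 50 - 33 = 17 subjects (34%) have no pair. Power is not the problem.

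**Step 3: the mean over all dosed subjects.** With n = 50 - k observed:
- M = [n x (-3.5) + k x d] / 50
- SS = (n - 1) x 36 + n x (-3.5 - M)^2 + k x (d - M)^2
- SD = sqrt(SS / 49)
- 95% CI = M ± 2.010 x SD / sqrt(50)

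Example, k = 10 and d = 0: M = -140/50 = -2.80; SS = 1404 + 19.6 + 78.4 = 1502; SD = 5.54; half-width 1.57.

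| Missing | Observed only | d = 0 | d = +3 (worse) |
|---|---|---|---|
| 5 | -3.50 (-5.30 to -1.70) | -3.15 (-4.79 to -1.51) | -2.85 (-4.56 to -1.14) |
| 10 | -3.50 (-5.42 to -1.58) | -2.80 (-4.37 to -1.23) | -2.20 (-3.89 to -0.51) |

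A fixed assigned value understates uncertainty, so the all-dosed intervals are slightly narrow.

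**Step 4: tipping point.** Find d for which the upper limit reaches zero.
- k = 5: d is about 11.1 points of worsening. Check: M = (-157.5 + 55.5)/50 = -2.04, half-width about 2.05.
- k = 10: d is about 5.0 points. Check: M = (-140 + 50)/50 = -1.80, half-width about 1.81.
- If the missing values also have SD 6, the figures are 10.7 and 4.4. If the observed SD is 3.48, the upper end of the range the plan cites, they are about 13.9 and 6.7.

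**Step 5: responders.** 0.70 x 45 = 31.5, taken as 31; 0.70 x 40 = 28. Exact (Clopper-Pearson) 95% intervals:

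| Missing | Observed only | All dosed, missing = non-response |
|---|---|---|
| 5 | 31/45 = 69% (53 to 82) | 31/50 = 62% (47 to 75) |
| 10 | 28/40 = 70% (53 to 83) | 28/50 = 56% (41 to 70) |

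**The case against.** The strongest case against has four parts.

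- **The loss will be visible.** SAP Section 6 tabulates disposition by population and reasons for early discontinuation, summaries report non-missing counts (Protocol Section 5.1: "descriptive statistics will include the number of non-missing observations"), and SAP Section 11 gives narratives for deaths. A reader could work out a rough worst-case rate. This stands, but a back-calculation is not a pre-specified estimate with an interval.
- **The denominator is an ambiguity, not a shown bias.** If Safety-set percentages use all Safety subjects, missing values already count as non-response. If they use non-missing values, they do not. This also stands: the text does not settle it, and one sentence would.
- **The responder endpoints are descriptive**, with no test or interval planned for any subject. An exact interval is therefore an improvement in its own right, not a consequence of missing data.
- **A larger limit is the uncontrolled pre/post comparison itself**, which no missing-data analysis repairs. That is true, and it is a separate matter.

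A reader might also infer more than the documents support:

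- *That incompletely dosed subjects vanish from efficacy.* They do not: the Safety-set repeat includes those with both scores.
- *That non-improvers or intubated subjects are excluded.* A fully dosed subject scored at Day 14 stays in as a non-responder, and Protocol Section 3.5.4 provides for modified QMG scoring in such circumstances.
- *That the protocol contradicts itself on the set for the responder rates.* Section 5.1.3 already sends efficacy to both sets; Section 5.1.3.2 needs only a clarifying line.

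**Conclusion.** The point holds as a gap worth fixing. Subjects who die or withdraw before Day 14 have no value in the primary mean change in either set, the protocol's Evaluable-set responder rates exclude them, and the Safety-set responder denominator is unstated.

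The direction of bias is likely but not certain: loss linked to poor outcome favours benefit, while a recovered subject may also miss the visit. The size cannot be derived from the documents. Under the assumptions above, 5 to 10 missing of 50 lowers a responder rate of about 70% by 7 to 14 percentage points, and moves the mean from -3.50 to -3.15 or -2.80 at zero change. That bears on interpretation, because the plan treats 3.5 points as the clinically significant change.

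The documents do not support the stronger conclusion that the primary test is unreliable. With 10 missing it fails only if those subjects worsen by about 5 points on average, and with 5 missing by about 11. The concern is about the estimates, not significance or power.

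**What to change.** In SAP Sections 5.2 and 10:

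1. Alongside the Evaluable-set rates, pre-specify the three Day 14 responder rates on all dosed subjects with the relevant baseline score. Count a missing Day 14 value, including after death, as non-response, and give an exact 95% CI. Make Protocol Section 5.1.3.2 agree with Protocol Section 5.1.3 and SAP Section 10 on the sets used.
2. For the primary mean change, pre-specify a sensitivity analysis on all dosed subjects with a Baseline QMG. Assign zero change, then increasing worsening until the conclusion changes (tipping point), to those missing Day 14, with deaths included. State that an Early Discontinuation QMG taken near Day 28 is not used as the Day 14 value.

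The cost is SAP wording and a few tables from data already collected. The reported all-dosed responder rate may be lower, and a recovered subject who misses the visit would count as a non-responder in that analysis. This is why it sits beside the Evaluable-set rate and does not replace it.

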### 5.1.2 Demographic and Baseline Characteristics

Demographic and baseline characteristics will be summarized using descriptive statistics.

### 5.1.3 Efficacy Analyses

Efficacy data will be summarized by visit on evaluable population and safety population (if different).

#### 5.1.3.1 Primary Efficacy Analyses

The primary efficacy variable is the change from Baseline in QMG score at Day 14. The primary efficacy variable will be summarized. A paired t-test (comparison between the pre and post) will be used to test for the treatment effect. The hypothesis test is to test the null hypothesis:  $H_0: \mu_d = 0$  versus alternative hypothesis  $H_a: \mu_d \neq 0$  where  $\mu_d$  is the mean change from Baseline to Day 14.

If the assumptions for parametric test are not met, the non-parametric test (Wilcoxon signed rank test) will be used.

#### 5.1.3.2 Secondary Efficacy Analyses

The following secondary efficacy variables will be summarized for evaluable population:

- Percentage of subjects who experience a clinical improvement assessed by QMG from Baseline (Day 0) to Day 14 where clinical improvement is defined as at least 3 point decrease in QMG
- Percentage of subjects who experience a clinical improvement assessed by MG-ADL from Baseline (Day 0) to Day 14 where clinical improvement is defined as at least 2 point decrease in MG-ADL
- Percentage of subjects who experience a clinical improvement assessed by the MG Composite from Baseline (Day 0) to Day 14 where clinical improvement is defined as at least 3 point decrease in the MG Composite

#### 5.1.3.3 Exploratory Efficacy Analyses

Summary statistics will be provided and paired t-test or Wilcoxon signed rank test will be used for testing the treatment effect at different visits for:

- Change in QMG score from Baseline (Day 0) to Day 7, Day 21 and Day 28
- Change in MG-ADL from Baseline (Day 0) to Day 7, Day 14, Day 21 and Day 28

- Change in MG Composite from Baseline (Day 0) to Day 7, Day 14, Day 21 and Day 28
- Change in AChR antibodies (or MuSK antibodies) from Baseline (Day 0) to Day 14 and Day 28
- Change in IgG levels from Baseline (Day 0) to Day 1 (after completion of infusion), Day 7, Day 14, Day 21 and Day 28

The number and percentage of subjects who experience a clinical improvement based on the following measures and at the following timepoints will be summarized.

- Clinical improvement in QMG score from Baseline (Day 0) to Day 7, Day 21 and Day 28 where clinical improvement is defined as at least 3 point decrease in QMG score
- Clinical improvement in MG-ADL from Baseline (Day 0) to Day 7, Day 14, Day 21 and Day 28 where clinical improvement is defined as at least 2 point decrease in MG-ADL
- Clinical improvement in MG Composite from baseline (Day 0) to Day 7, Day 14, Day 21 and Day 28 where clinical improvement is defined as at least 3 point decrease in MG Composite

The number of subjects who need ICU admission, the length of ICU stay, need for intubation, and length of intubation will be collected and summarized.

#### 5.1.4 Safety Analyses

The safety analysis will be based on safety population.

The safety analyses will be addressed by listing and tabulation of AEs (includes suspected ADRs), vital signs, physical assessments and clinical laboratory tests. Data will be described using descriptive analyses.

- Adverse events:

Safety analysis will be primarily focused on a descriptive analysis of suspected ADRs. Safety assessment will be based on the prevalence of suspected ADRs that occurred during the clinical trial.

Adverse events will be coded and classified using MedDRA® terms (system organ class and preferred terms).

Adverse events will be classified as TEAEs or non-TEAEs depending on the comparison of AE onset date/time with the start date/time of study treatment with the IP. A TEAE will be defined as an AE which occurs between the beginning of the first infusion of IGIV-C and the final visit of the clinical trial. A non-TEAE will be defined as an AE which occurs prior to the 1st dose of IP. Non-TEAEs and TEAEs will be summarized separately.

All AEs will be summarized by presenting subject incidences and percentages, and they will also be listed by body systems with subject identification codes.

In addition, TEAEs, including suspected ADRs, will be summarized, system organ class, preferred term, causal-relationship, intensity (severity) and seriousness (serious vs. non-serious) using descriptive statistics. At each level of summarization, a subject will only be counted once per system organ class or preferred term using the most severe or causal relationship AE.

AEs temporally associated to the infusion of the IP (i.e., infusional AEs, including infusional suspected ADRs), will be summarized by presenting infusion/subject incidences and percentage and listed. In addition, the infusion rate in effect at the time of onset of the AE, the time the AE is first reported and the time the AE changes materially in intensity and/or resolves will be also reported and listed.

Subjects with deaths, SAEs, suspected ADRs and AEs leading to premature discontinuation from the study will be listed and presented in a narrative form.

AEs for which the Investigator causality assessment is missing or undetermined will be individually listed.

- Vital signs:  
Vital signs (T, RR, HR, SBP and DBP) will be listed for each clinical trial subject. Abnormal vital signs judged as clinically relevant by the Investigator will be considered AEs. In case a subject presents a clinically relevant abnormality of vital signs during an infusion, the event will be flagged and reported as an AE temporally associated to the infusion. For each subject and for each infusion, every vital sign will be considered. Clinical relevance will be based on the Investigator's criteria.
- Physical Assessment:  
Physical Exam findings (normal and abnormal) will be listed for each clinical trial subject. Abnormal findings judged as clinically relevant by the Investigator will be considered AEs.
- Blood biochemistry and hematology:  
All clinical laboratory data for renal (creatinine, BUN), hepatic (ALT, AST, ALP, and TBL) and haematological parameters (CBC including differential leukocyte count) will be listed for each clinical trial subject. Laboratory results out of the normal range judged by the Investigator as clinically relevant will be considered AEs.
- Lab tests for TEs and hemolysis:  
The D-dimer for TE assessment and the laboratory tests for detecting hemolysis (including whole blood hemoglobin, serum or plasma free hemoglobin, haptoglobin, LDH, DAT, ARC, RBC, hematocrit, TBL and indirect bilirubin, and blood smear) will be listed and out of normal range results will be flagged.

